9. EVALUATION OF ADVERSE EVENTS

Only serious adverse events (SAEs) will be captured in this study.

9.1. Serious Adverse Events (SAEs)

An adverse event will be classified as serious if it meets any of the following criteria:

- Results in, leads to, or contributes to, a death;
- Is life-threatening;
- Results in permanent disability or incapacity (i.e., permanent impairment of a body function or permanent damage to a body structure);
- Requires in-patient hospitalization or prolongs hospitalization;
- Necessitates medical or surgical intervention to preclude a permanent disability or incapacity;
- Results in fetal distress, fetal death or a congenital anomaly/birth defect.

9.2. Anticipated and Unanticipated Serious Adverse Events

The investigator will assess each serious adverse event for whether it is anticipated or unanticipated using the definitions below.

9.3. Heart Graft Related SAEs

Heart Graft Related SAEs (HGRSAEs) are defined as

- Moderate or Severe primary heart graft dysfunction (PGD) (left or right ventricle) (not including rejection or cardiac tamponade) according to ISHLT consensus manuscript.
- Primary graft failure requiring re-transplantation.

Heart-graft related SAEs will be collected from the time a subject is transplanted with the OCS™ heart until the completion of the 30-day follow-up evaluation. A HGRSAE will be followed until resolution or stabilization of the event.

9.4. Unanticipated Adverse Device Effect (UADE)

An UADE means any serious adverse effect on health or safety or any life-threatening problem or death caused by, or associated with, a device, if that effect, problem, or death was not previously identified or encountered before at least once in standard clinical practice, in nature, severity, or degree of incidence in the investigational plan or application (including a supplementary plan or application), or any other unanticipated serious problem associated with a device that relates to the rights, safety, or welfare of subjects.

Anticipated serious adverse events are associated with heart transplant procedures and have been documented within the first 30 days after heart transplant. The list of events includes, but is not limited to:

- Acute rejection

- Atrial and ventricular arrhythmias
- Bleeding (major)
- Hemodynamic instability
- Death
- Fever
- Primary Graft Dysfunction
- Respiratory failure
- Graft failure
- Sepsis
- Renal dysfunction
- Hyperammonaemia
- Malignancy (post-transplant lymphoproliferative disorder (PTLD))
- Multiple organ failure
- Myocardial infarction
- Neurological dysfunction
- Hepatic dysfunction
- Diabetes due to steroid and anti-rejection medications
- Gall stones
- Pancreatitis
- Peptic ulceration
- Gastritis
- Gastro esophageal reflux disease (GERD)
- Aspiration
- Cardiac tamponade
- Pneumo-mediastinum
- Pneumothorax
- Hemothorax
- Pleural bleeding
- Pleural effusion
- Venous thromboembolism (deep venous thrombosis [DVT])
- Pulmonary embolism (PE)

- Sternal wound dehiscence
- Organ deemed not transplantable after retrieval
- Stroke
- Psychosis
- Cerebrovascular accident
- Peripheral vascular clotting or occlusion due insertion of mechanical support
- Limb gangrene due to vascular occlusion due insertion of mechanical support
- Use of mechanical circulatory support
- Coagulopathy
- Hyperacute rejection
- Anastomotic site complications; narrowing, bleeding or occlusion
- Delayed sternal wound closure due to compromised cardiac function or excessive bleeding or both
- Bowel thromboembolic complications and gangrene
- Protamine and other anti-heparin medication reaction
- Heparin induced thrombocytopenia.

9.5. Reporting of Adverse Events

All SAE information will only be collected from transplant through day 30. Unanticipated adverse device effects (UADE) should be reported to TransMedics, Inc., within 48 hours of the time the investigator learns of the event, but in no case later than 5 working days after learning of the event.

SAEs should be entered into the study database as soon as possible. SAE will be followed until the investigator designates the event to be either resolved or its effect on the patient's condition stabilized. Details related to treatment of the SAE will also be collected.

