6.3. Subject Enrollment and Screen Failures

As part of the screening process, the following must occur:

- Subject must be matched with a donor heart that meets eligibility criteria for Heart EXPAND CAP; and
- Subject must meet eligibility criteria for Heart EXPAND CAP; and
- The matched donor heart must be accepted for transplantation in the donor chest by the transplant surgeon or designee; and
- The matched donor heart must be instrumented on the OCS.

A subject will be considered a screen failure under the following conditions:

- The donor heart matched to this recipient fails to meet transplantability criteria per [Section 7.4](#) of the protocol following OCS Heart System instrumentation (i.e., donor heart turndown).
- The recipient fails to meet inclusion/exclusion criteria on the day of the potential transplant after an eligible donor heart is instrumented on the OCS™ Heart System and accepted for transplantation following OCS instrumentation preservation.
- Logistical reasons prevent transplantation of donor heart instrumented on the OCS™ Heart System that meets acceptance criteria for transplant following OCS preservation (e.g., transplant center or OPO issues, transportation or allocation issues, surgeons or ORs are unavailable).

A subject will be considered enrolled when the subject is transplanted with the OCS-instrumented organ.

Subjects who are screen failures that remain eligible for the study will return to the waiting list for another heart transplant. Depending on the donor match, this next transplant may be either in the Heart EXPAND CAP or the subject may be transplanted using standard cold storage and will not be enrolled in this study.

Medicare beneficiaries with a clinical need for transplantation will be treated in the same manner as patients not covered by a Medicare plan. The rules of participation and results of the study apply to Medicare and non-Medicare covered patients in the same manner.

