7.4.2. Reject for Transplantation

Donor hearts preserved on the OCS will be rejected for any of the following:

- Transplanting surgeon and/or designee is clinically unsatisfied with donor heart condition/performance on the OCS Heart System at final evaluation, e.g., unstable and rising arterial lactate despite multiple maneuvers to optimize perfusion parameters (increasing AOP and/or CF)
- Final arterial perfusate lactate ≥ 5 mmol/L.

Any decision to turndown hearts after preservation and assessment on OCS™ Heart System should be documented on the appropriate CRF. Samples should be sent to the central core lab for assessment of any inherent cardiac pathology that was not diagnosed at retrieval of the donor heart.

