11.1. Potential Risks

The potential risks to subjects from participation in this clinical trial include the following:

- **Potential Risks Associated with Heart Transplant Procedures:** These risks include post-operative complications not associated with the OCS™ Heart device such as graft failure, primary graft dysfunction, rejection, infection and other organs/systems complications, graft vessel disease (an expression of chronic rejection), infection, abnormal kidney function, diabetes, high level of cholesterol, high blood pressure, cancer and neurological complications.
- **The Potential Risks Associated with OCS Heart System:** Subjects have the risk of not receiving organs preserved with the OCS Heart System under certain conditions including: (1) the OCS Heart System may not work properly, or there may not be personnel available trained in the use of the Heart System or (2) the OCS Heart System may malfunction, or the medical staff may make an error which could lead to damage of the donor heart. If this occurs, the subject will have to wait for a new donor heart to become available. As with any medical device, there is always a risk of extremely rare or previously unknown side effects developing from the treatment.
- **Potential Risk of Using a Donor Heart that is Unsuitable for Transplantation:** Regardless of the preservation system that is used, there is the risk that a patient can receive a heart that does not adequately function. This trial is designed to utilize hearts that would not be accepted for transplantation using cold storage preservation. There is the possibility that using such hearts may increase the risk of transplanting a heart that does not function appropriately. It is also possible that the donor heart may not meet transplantability criteria after OCS preservation and would be turned down for transplant. In the EXPAND trial, only 19.4% of the donor hearts were turned down following OCS preservation so the anticipated frequency of this event is low.

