APPENDIX 2. SCHEDULE OF CLINICAL ASSESSMENTS

Evaluations	Donor & Heart Assessments	
	Acceptance	OCS Preservation
Eligibility & ID	X	
Demographics/Characteristics	X	
Donor Cause of Death	X	
Donor Medical & Social History	X	
Donor Heart Assessment	X	
Donor Cross Clamp Time	X	
OCS Preservation Parameters		X
OCS Lactate Levels		X
Device Malfunction (if applicable)		X
Non-transplant Reasons (if applicable)		X

Evaluations	Recipient Schedule of Assessments							
	Day of Tx	T0*	T24	Discharge	Day 30	Mo 6	Mo 12	
Eligibility & Informed Consent	X							
Demographics/ Characteristics	X							
Medical & Cardiac History	X							
Transplant Details	X							
PGD Scores			X					
Inotropic Support		X	X					
Right Heart Catheter Results		X**	X**					
Mechanical Circulatory Support		X	X					
Patient & Graft Survival		X	X	X	X	X	X	
Echocardiogram			X	X				
Initial ICU Stay				X				
Initial Hospital Stay				X				
HGRSAEs and SAEs	X	X	X	X	X			
Cardiac Allograft Vasculopathy								X**

*T0 is defined as the time of initial admission to ICU immediately post-heart transplant procedure within a 2 hour window.

**ONLY Tests regularly scheduled per center standard of care or performed due to a clinical cause at these time-points will be collected.

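### Every planned safety result is limited to transplanted recipients, so a donor heart lost to device malfunction or user error, a risk named in Section 11.1, cannot appear in any of them

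*Combined protocol and SAP*

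**What the plan says.** **The risk.** Under the risks of the OCS Heart System, Section 11.1 warns that "the OCS Heart System may malfunction, or the medical staff may make an error which could lead to damage of the donor heart", and adds that the subject must then wait for a new heart.

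**Who is followed.** Section 6.3: "A subject will be considered enrolled when the subject is transplanted with the OCS-instrumented organ". A candidate whose matched heart is turned down after instrumentation is a screen failure. If still eligible, that candidate returns to the waiting list.

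**What is collected.** Section 9.5: "All SAE information will only be collected from transplant through day 30". Section 9.3 says that heart graft-related SAEs "will be collected from the time a subject is transplanted" with the OCS heart. Section 9.4 lists "Organ deemed not transplantable after retrieval" among the anticipated SAEs.

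**What is analysed.** Section 10.2.1 assigns every effectiveness and safety endpoint except donor heart utilization to the transplanted recipient population. Section 10.4 analyses heart graft-related SAEs per subject. Section 10.4.1 tabulates device-related SAEs, unanticipated SAEs and deaths. The Section 15.8 stopping rule uses 30-day deaths among recipients of an OCS heart.

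**What is recorded elsewhere.** Malfunctions go to the sponsor, which investigates them (Section 12.4). Turndowns go on a CRF (Section 7.4.2). Appendix 2 schedules both device malfunction and non-transplant reason during OCS preservation.

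**The concern.** The stated objective is to add evidence on the safety and effectiveness of the device. As planned, the safety evidence is conditional on the device having delivered a heart that was transplanted. If more hearts were lost to malfunction or user error, the heart graft-related SAE endpoint, the device-related SAE table and the stopping rule would not change. The utilization rate would fall, but nothing in Section 10 would show whether the cause was the device, the donor, the recipient or logistics.

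The documents also conflict with themselves. Section 9.4 treats an organ found untransplantable after retrieval as an SAE. For a turndown on the OCS, that event happens before the Section 9.5 window opens, and to someone who is not enrolled.

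**Working it through.** **Step 1. Follow one lost heart through the plan.** A consented candidate is matched, the heart is instrumented, and a malfunction or user error makes it unusable.

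| Planned output | Who is counted | Is the event visible? |
|---|---|---|
| Heart graft-related SAEs (9.3, 10.4) | Transplanted recipients, from transplant | No |
| Device-related and unanticipated SAEs, deaths (10.4.1) | Subjects, enrolled at transplant; SAEs from transplant (9.5) | No |
| Stopping rule (15.8) | Recipients of an OCS heart | No |
| Donor heart utilization (10.2.2, 10.3.2) | All instrumented hearts | Yes, as a failure without a cause |

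Widening the SAE window alone would not close the gap, because Section 10.2.1 would still exclude the candidate.

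**Step 2. Reproduce the plan's figure.** Section 2.2.3 gives 93 hearts preserved on OCS in EXPAND, of which 75 were transplanted.

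- Utilization: 75/93 = 80.6%, as stated. Exact 95% CI 71.1% to 88.1%.
- Not transplanted: 93 − 75 = 18, and 18/93 = 19.4%, as stated in Section 11.1. Exact (Clopper-Pearson) 95% CI 11.9% to 28.9%.

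**Step 3. Hearts outside the safety analyses here.** The target is 75 transplanted recipients (Section 4.2). With utilization u, the expected number of hearts instrumented but not transplanted is 75/u − 75.

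- u = 75/93: 93 − 75 = 18. The 95% negative binomial prediction range at this u is 9 to 28.
- u = 88.1%: 85.1 − 75 = about 10.
- u = 71.1%: 105.4 − 75 = about 30.

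**Step 4. What the safety tables would show.** The documents give no device or user share, so the counts below are assumptions, out of 93 instrumented hearts.

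| Assumed losses to device or user | Share of 93 | Exact 95% CI | Lost hearts shown in safety results |
|---|---|---|---|
| 0 | 0% | 0% to 3.9% | 0 |
| 1 | 1.1% | 0.03% to 5.8% | 0 |
| 3 | 3.2% | 0.7% to 9.1% | 0 |
| 5 | 5.4% | 1.8% to 12.1% | 0 |
| 9 | 9.7% | 4.5% to 17.6% | 0 |

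The last column is the same in every row, so the planned safety results cannot distinguish these cases.

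**The case against.** The strongest reply is that the information is not lost. Malfunctions are reported and investigated, turndowns are documented, and both malfunction and non-transplant reason are scheduled fields. This stands. A reader might infer that the event goes unrecorded, and the documents do not support that: it is not recorded as an SAE and is not part of any planned safety analysis.

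Other replies stand in part.

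- **General summary rule.** Section 10.1 says that categorical variables are summarized by frequencies and percentages. That describes how a variable is presented. It does not bring these events into a safety analysis.
- **UADE reporting.** It has no stated transplant window, and UADEs reach the sponsor and the IRB (Sections 9.5 and 14.2). The Section 9.4 definition includes an unexpected degree of incidence, so a rising malfunction rate could qualify. A single loss of a kind already named in the plan would generally not, and no UADE table is planned.
- **DSMB.** It may request more information (Section 15.8), but nothing requires these data to be sent to it.
- **Protection of the candidate.** Section 11.2 says that the recipient should undergo no procedure until the heart is accepted. That limits surgical harm but does not address the loss of the heart.
- **Hearts that are damaged but still transplanted.** Their consequences can appear, for example as graft dysfunction. The gap concerns hearts that are lost.

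Three stronger readings are tempting and fail.

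- A reader might take 19.4% as a device-harm rate. The sentence "only 19.4% of the donor hearts were turned down following OCS preservation so the anticipated frequency of this event is low" stands in the Section 11.1 item on unsuitable donor hearts, not in the malfunction item, and covers all causes. Its wording needs no edit for this point, because the figure is in the same sentence.
- A reader might apply the waiting-list death rates in Table 1 to a turned-down candidate. Those rates run from listing and cover all registrations. They are neither the risk after a turndown nor an increase caused by one.
- A reader might infer that core-lab review favours the device because Section 7.4.2 directs samples to "assessment of any inherent cardiac pathology that was not diagnosed at retrieval of the donor heart". Looking for donor disease and finding none removes the donor explanation, so the review can count against the device too.

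**Conclusion.** The concern holds as a gap in analysis, together with one internal inconsistency. Enrolment at transplant, SAE collection from transplant, a safety population of transplanted recipients and a stopping rule on the same group jointly exclude the lost-heart risk named in Section 11.1 from every planned safety result.

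About 18 instrumented hearts would lie outside those results, with a range of roughly 9 to 30 across the calculations above. This assumes that EXPAND utilization carries over; Section 2.7 describes the eligibility criteria as identical. The number counts hearts, not people: in PROCEED II five declined hearts involved four patients (Section 2.3.8). It is an upper limit on device or user losses, not an estimate of them. PROCEED II also shows that declined hearts can be reported by cause: four for rising lactate and one for friable aortic tissue.

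The study is descriptive and has no statistically determined sample size, so no hypothesis test is affected. What is affected is whether its safety report covers a risk that the protocol itself names.

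**What to change.** 1. **Sections 10.2 and 10.4.1.** Add a safety analysis on the OCS heart population. Give the number, percentage and exact 95% CI of instrumented hearts with a device malfunction or user error, whether or not the heart was transplanted. Give the same for hearts not transplanted, by recorded reason: device or user, perfusion or lactate criteria, donor pathology, recipient, logistics.
2. **Section 15.8.** Include this table in the DSMB reports.
3. **Sections 9.4 and 9.5.** Reconcile the list item on untransplantable organs with the collection window, either by removing the item or by stating where the event is recorded and analysed.
4. **Optional.** After a turndown, record later transplant, death or delisting of the matched consented candidate.

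**Cost.** Items 1 to 3 need protocol wording and one table, built mainly from fields already on the Appendix 2 schedule. User error is not a separate item there, so a response category may have to be added. Item 4 adds a small amount of follow-up in people who are not enrolled, and the main change does not depend on it. The safety profile may look less favourable. No clinical rule changes.

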9.5.1. Relationship of an Adverse Events to OCS™ Heart

The investigator will assess the relationship of the serious adverse event to the OCS™ Heart System. The relationship will be assessed using the following categories:

- **Definitely Related:** There is a reasonable causal and temporal relationship between preservation with the OCS™ Heart and the adverse event.
- **Probably Related:** It is more likely than not that there is a reasonable causal relationship between preservation with the OCS™ Heart and the adverse event.
- **Possibly Related:** There is a reasonable relationship with preservation with the OCS™ Heart and the adverse event, but the causal relationship is unclear or lacking.

- **Unlikely Related:** There is a temporal relationship with preservation with the OCS™ Heart and the adverse event, but there is not a reasonable causal relationship between the OCS™ Heart and the event.
- **Unrelated:** There is no relationship between preservation with the OCS™ Heart and the adverse event.

9.5.2. Severity

The investigator will rate the severity of the serious adverse event using the following categories:

- **Mild:** The adverse event is transient and/or easily tolerated by the subject.
- **Moderate:** The adverse event causes the subject discomfort and interrupts the subject's usual activities.
- **Severe:** The adverse event causes considerable interference with the subject's usual activities.

9.5.3. Pre-Existing Conditions

Pre-existing diseases or conditions will not be reported as adverse events.

10. STATISTICAL METHODS

10.1. General

Continuous variables will be summarized using descriptive statistics, specifically the mean, median, standard deviation, minimum, and maximum. Categorical variables will be summarized using frequencies and percentages.

10.2. Analysis Populations

10.2.1. Transplanted Recipient Population

The transplanted recipient population will consist of all recipients transplanted with OCS Heart-preserved donor hearts. The analyses of all effectiveness and safety endpoints, except the rate of donor hearts utilization that were successfully transplanted after preservation and assessment on the OCS Heart System, will be based on the transplanted recipient population.

10.2.2. OCS Heart Population

The OCS heart population will consist of all donor hearts that are instrumented on the OCS. The analysis of the rate of donor hearts utilization that were successfully transplanted after preservation and assessment on the OCS Heart System will be based on the OCS heart population.

10.3. Statistical Analysis

10.3.1. Primary Endpoint

The primary endpoint will be summarized using counts and percentages and an exact 95% confidence interval for the true percentage based on the binomial distribution.

10.3.2. Secondary Endpoints

Each secondary effectiveness endpoint will be summarized using counts and percentages and an exact 95% confidence interval for the true percentage based on the binomial distribution. The first two secondary effectiveness endpoints will be analyzed using the transplanted recipient population.

The rate of donor hearts that were successfully transplanted after preservation and assessment on the OCS Heart System (i.e., donor heart utilization), will be analyzed using the OCS heart population.

10.3.3. Other Endpoints

Other endpoints for this trial include:

- Patient survival at 6 and 12 months post-transplant
- Incidence of primary graft failure requiring re-transplantation through 12 months post-transplant
- Duration of initial post-transplant ICU stay
- Duration of initial post-transplant hospital stay

Each endpoint will be summarized using counts and percentages and an exact 95% confidence interval for the true percentage based on the binomial distribution.

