Statistical Methods	
The transplanted recipient population will consist of all recipients who are transplanted according to this protocol. The analyses of all effectiveness and safety endpoints, except the rate of donor heart utilization, will be based on the transplanted recipient population.
 
The OCS heart population will consist of all donor hearts that are instrumented on the OCS Heart System. The analysis of the rate of donor heart utilization that were successfully transplanted after preservation and assessment on the OCS Heart System will be based on the OCS heart population.
 
The primary endpoint will be summarized using counts and percentages and an exact 95% confidence interval for the true percentage based on the binomial distribution.
 
Each secondary effectiveness endpoint will be summarized using counts and percentages and an exact 95% confidence interval for the true percentage based on the binomial distribution. The first two secondary effectiveness endpoints will be analyzed using the transplanted recipient population.
 
The rate of donor hearts that were successfully transplanted after preservation and assessment on the OCS Heart System (i.e., donor heart utilization), will be analyzed using the OCS heart population.
 
Safety will be analyzed principally by examination of the frequency of adverse events. In particular, the number of heart graft-related serious adverse events (HGRSAEs) up to the 30-day follow-up after transplantation per subject will be analyzed. This endpoint is defined to consist of the following adverse events (at most one per type), if they are serious adverse events:
 
 Moderate or severe primary heart graft dysfunction (PGD) (left or right ventricle) (not including rejection or cardiac tamponade) according to ISHLT consensus manuscript (as defined in Appendix 1 of the protocol). Primary graft failure requiring re-transplantation.

[figure not shown]
	This endpoint will be summarized using descriptive statistics, specifically the mean, median, standard deviation, minimum, maximum, and a 95% confidence interval for the mean based on the t-distribution.
Determination of Sample Size	This is a continued access protocol and does not have a statistically determined sample size
Trial Sponsor	TransMedics, Inc. [name]

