4.2. Trial Size and Subject Follow-up

This trial will be conducted at up to 8 institutions, in the United States and will include 75 transplanted heart recipients. The number of subjects was determined based on the enrollment rate for Heart EXPAND and following FDA guidelines for CAPs.

Subjects will be followed for 12 months from the date of transplantation (some of which will be post-market). The summary of follow-up assessments are is summarized in [Appendix 2](#):

- All subjects will be followed from transplant to discharge.
- Patient and graft survival will be documented at Day-30 post transplant.
- Subjects will be followed at 6 and 12 months post-transplant as summarized in Appendix 2.

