8. TRANSPLANT, IMMEDIATE POST-OPERATIVE AND LONG TERM FOLLOW-UP

8.1. Transplant Details

The following information concerning the transplant procedure will be collected:

- The organ recipient unique post-transplant patient identifier
- Total cross clamp duration in minutes (from donor cross-clamp application to removal of cross-clamp in the recipient)
- Pre-OCS cold ischemia time (time from donor cross clamp until start of perfusion on OCS)
- Post-OCS cold ischemia time (time from heart flush on OCS until aortic cross-clamp removal in the recipient)
- Any surgical complications encountered during surgery.

8.2. Post Transplant Functional Assessments Day 0 – Day 30:

- Heart Primary Graft Dysfunction (PGD) Surveillance in the first 24 hours (see [Appendix 1](#))
- Initial use of Mechanical Circulatory Support
- Inotropic Support for first 24 hours: the following inotropic medication doses, if available, will be collected at ICU admission T0 and T24 hours after ICU admission post-heart transplantation:
 - Dopamine – mcg/kg/min
 - Dobutamine – mcg/kg/min
 - Amiodarone – mcg/kg/min
 - Milrinone – mcg/kg/min

- Epinephrine – mcg/kg/min
- Norepinephrine – mcg/kg/min
- Echocardiogram results in the first 24 hours
- Right Heart Catheter Data between ICU admission T0 and T24 hours after ICU admission post-heart transplantation (not required; collected only if performed as part of the institution's standard of care):
 - Pulmonary Artery Pressures (PAP)
 - Pulmonary Capillary Wedge Pressure (PCWP)
 - Cardiac index (CI)
 - Right Atrial Pressure (RAP)
 - Initial Post-Transplant ICU Stay
- Initial use of Mechanical Respiratory Support
- Initial Post-Transplant Hospital Stay
- Immunosuppression Medications
- Trans-thoracic echocardiogram prior to Discharge
- Patient and Graft Survival at Day 30 (+5 days), patient and graft survival will be assessed.
- Serious Adverse Events: All SAEs will be collected for the first 30 days post-transplant. SAEs will be followed until the investigator designates the event to be either resolved or its effect on the patient's condition stabilized.

8.3. Long Term Follow-up: 6 and 12 months:

Follow-up data collection will be conducted at 6 and 12 months post transplant. Although the follow-up may be done via phone contact; medical records may be needed for additional information.

- **6-Month Follow-Up:** At 6 months post transplant (\pm 30 days), the patient will be evaluated for:
 - Patient and graft survival

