 - Whether the patient was re-hospitalized after initial discharge, and, if so, the primary reason for the hospitalization and the length of stay
 - Information will also be collected on any diagnosis of cardiac dysfunction and, if so, the method of diagnosis and treatment.
- **12-Month Follow-Up:** At 12 months (\pm 30 days) post transplant, the patient will be evaluated for:
 - Patient and graft survival
 - Any diagnosis of cardiac allograft vasculopathy and, if so, the method of diagnosis (e.g., IVUS, coronary angio).

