15.3. Periodic Monitoring Visits

Monitoring visits will be conducted as scheduled by the sponsor. The monitor should visit each site as needed to ensure the following:

- Facilities continue to be adequate and acceptable.
- Informed consent has been obtained.
- The protocol is being properly followed.
- The IRB has approved or been notified of any protocol changes.
- Accurate, complete and current records are being maintained, and the information recorded and submitted to the Sponsor is representative of the subject's record and other supporting documentation.
- Accurate, complete and timely adverse event reports are being submitted to the Sponsor.
- The reason for a subject's withdrawal from the trial has been documented.
- Reports are being submitted to the IRB and Sponsor.
- The appropriate staff is carrying out trial activities.

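### Does Section 10.3.3 need a rule for recipients whose status at 6 or 12 months is unknown?

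*Combined protocol and SAP*

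**What the plan says.** Section 10.3.3 lists four other endpoints. They include patient survival at 6 and 12 months and "Incidence of primary graft failure requiring re-transplantation through 12 months post-transplant". The analysis is one sentence: "Each endpoint will be summarized using counts and percentages and an exact 95% confidence interval for the true percentage based on the binomial distribution".

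Section 10.2.1 sets the denominator: "The transplanted recipient population will consist of all recipients transplanted with OCS Heart-preserved donor hearts". The Synopsis agrees: "The analyses of all effectiveness and safety endpoints, except the rate of donor heart utilization, will be based on the transplanted recipient population".

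Follow-up lasts 12 months for every recipient (Synopsis, Follow-up; Section 4.2), and part of it may fall after marketing approval. Section 8.3 sets contacts at 6 and 12 months, each with a 30-day window either side, and allows for remote contact: "Although the follow-up may be done via phone contact; medical records may be needed for additional information". Section 14.2 requires a death to be reported to the sponsor within 48 hours of the investigator learning of it. Section 15.3 has the monitor check that the reason for a subject's "withdrawal from the trial has been documented".

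Nothing in Section 10 mentions missing status, withdrawal, censoring or imputation. Section 10.5 states that the sample size was not set by statistical methods.

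**The concern.** A binomial proportion over all transplanted recipients needs each one classed as event or non-event at the time point. If a recipient has withdrawn or cannot be reached, Section 10.3.3 leaves three readings open: count as event-free, count as an event, or leave out. The same data would then give different figures, and the choice could be made after the data are seen. Kaplan-Meier and cumulative incidence use each recipient up to the last date known alive, so they avoid that classification.

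These are the longest-term endpoints in the protocol. Section 2.3.11 also reports an apparent survival decrease for OCS recipients over long follow-up in PROCEED II, so the 12-month figure is likely to be read closely.

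**Working it through.** **Is there a planned figure to reproduce?** No. The plan gives no target, power or loss rate for these endpoints. The figures below borrow EXPAND results and assume a loss.

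**Inputs**
- N = 75 (Section 4.2).
- EXPAND 6-month survival 66/75 = 88.0%, so 75 − 66 = 9 deaths (Section 2.2.6, Table 4).
- Two further deaths between 6 and 12 months, so 9 + 2 = 11 (Section 2.2.6). This count is incomplete: 12-month follow-up was then available for 40 of 75. It serves only as a plausible event count.
- One re-transplantation in 75 (Section 2.2.7).
- Unknown status: assumed 4 to 8 of 75. No document supports a particular number.

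**No unknowns.** All readings agree: 64/75 = 85.3% (exact 95% CI 75.3 to 92.4, about 17 points wide). The error is zero.

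**12-month survival with unknowns**

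| Unknown | Counted alive | Left out | Counted dead |
|---|---|---|---|
| 4 | 64/75 = 85.3% | 60/71 = 84.5% (74.0 to 92.0) | 60/75 = 80.0% (69.2 to 88.4) |
| 8 | 64/75 = 85.3% | 56/67 = 83.6% (72.5 to 91.5) | 56/75 = 74.7% (63.3 to 84.0) |

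The gap between best and worst case is 1/75 = 1.33 points per unknown: 5.3 points for 4 and 10.7 for 8.

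**Kaplan-Meier on the same data.** If the loss falls just after month 6 and the two late deaths follow:
- 4 lost: 0.88 × 60/62 = 85.16%. Leaving out gives 84.51%, which is 0.65 points lower.
- 8 lost: 0.88 × 56/58 = 84.97%. Leaving out gives 83.58%, which is 1.38 points lower.

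If the loss comes after both late deaths, Kaplan-Meier is 0.88 × 64/66 = 85.33%, and leaving out is 0.83 points (4 lost) or 1.75 points (8 lost) lower.

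**6-month survival, 9 deaths.** Leaving out gives 62/71 = 87.3% for 4 unknown and 58/67 = 86.6% for 8, against 88.0% with none. Counting unknowns dead gives 62/75 = 82.7% and 58/75 = 77.3%.

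**Re-transplantation, one event.** Counted event-free: 1/75 = 1.3% (upper limit 7.2%). Left out: 1/71 = 1.4% (7.6%) or 1/67 = 1.5% (8.0%). Counted as events: 5/75 = 6.7% or 9/75 = 12.0%. The last reading supposes that every unreachable recipient was re-transplanted.

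**How likely is unknown status?**
- EXPAND reported 6-month survival with the full denominator of 75 (Section 2.2.6).
- PROCEED II was designed for at most 30 days of follow-up. The sponsor still assembled long-term survival data on 118 + 12 = 130 patients from the registry and the sites (Section 2.3.11), which equals the 130 in the intent-to-treat population (Section 2.3.4).
- This protocol is US-only, and the registry described in the footnote to Section 2.3.11 covers US recipients. Sections 7.3 and 8.1 record donor and recipient identifiers. The protocol does not commit to a registry look-up.

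**Would replacing the estimator be free of trouble?** No. A scheduled 12-month contact may fall 30 days early, on day 335. Suppose 32 of 64 survivors are last seen alive on days 335 to 364 and are censored there, and both late deaths come afterwards. Kaplan-Meier then gives 0.88 × 32/34 = 82.8% instead of 85.3%, although no one was lost. A further rule on the visit window would be needed.

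**The case for a change.** The strongest argument for a change is that fixing the denominator at all transplanted recipients does not fix the numerator: an unknown who stays in must still be called alive or dead. With 8 unknowns, one dataset could be reported as anything from 85.3% to 74.7%. Withdrawal is foreseen in Section 15.3, and prompt death reporting does not help once contact is lost. The document itself states a missing-value method for PROCEED II (Section 2.3.5) and uses Kaplan-Meier there (Section 2.3.11), yet Section 10 has neither. A few added lines would cost little.

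The textual point stands. The estimate of harm is weaker. The 10.7-point span requires a loss that nothing in the documents supports, and it compares two extreme conventions that an analyst would normally show as bounds, not adopt as the result. The line in Section 15.3 is a general monitoring item, and follow-up continuing after approval does not mean that it lapses. For re-transplantation, calling the effect negligible is fair only when unknowns are left out or counted event-free; the worst-case bound is wide. That bound reflects how rare the event is, and a competing-risk estimate for about one expected event would add little.

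**Conclusion.** No change follows. Section 10.3.3 omits a rule for unknown status, but with complete follow-up the planned exact binomial proportion is the right summary. The sponsor's record in EXPAND at 6 months and in PROCEED II makes near-complete vital status likely.

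Under an assumed loss of 4 to 8 of 75, leaving unknowns out differs from Kaplan-Meier by 0.65 to 1.75 points, roughly a tenth of the interval width at most. The endpoints are descriptive, carry no hypothesis test and drive no decision rule in the plan. An analyst who met a few unknowns would report their number and give a censored estimate or bounds, methods the sponsor already knows.

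This conclusion rests on loss being small. The 11 deaths are illustrative, because they come from incomplete 12-month follow-up in EXPAND. Heavy loss of status would matter more, at 1.3 points per unknown between the extreme readings, but nothing in the documents suggests it.
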